## 2 INTRODUCTION

[figure not shown]
### 2.1 Study Rationale

Lupus nephritis (LN) is one of the most serious manifestations of systemic lupus erythematosus (SLE). Approximately 38% of patients have LN at the time of SLE diagnosis and 10 to 20% of them may progress to end-stage renal disease. Lupus nephritis confers an almost 3-fold higher risk of death than SLE without LN.

[figure not shown]
Despite advances in medical care, the prognosis for patients with LN has not substantially changed since the 1980s. Although the current standard of care treatments may result in a little more than half the patients showing some improvement in certain markers of disease activity (such as proteinuria, serum creatinine, hematuria, and urinary casts), long-term maintenance therapies are known to have toxic side effects and disease relapse is common. There remains an unmet need for novel, well tolerated orally administered therapies that can effectively modify the disease course and control symptoms.

[figure not shown]

[figure not shown]

[figure not shown]

[figure not shown]
### 3 OBJECTIVES AND ENDPOINTS

Objective	Endpoint
Primary – 52-week Blinded Treatment Period (Part B)	

 
Safety: To assess the safety and tolerability of BMS-986165 in subjects with LN
 
	
 
AEs, vital signs, ECGs, and laboratory abnormalities from baseline through Week 52
 

 
Efficacy: To evaluate the efficacy of BMS-986165 compared with placebo with regard to proteinuria
 
	
 
Percentage change from baseline in 24-hour UPCR at Week 24
 

Secondary– 52-week Blinded Treatment Period (Part B)	

 
Efficacy: To evaluate the efficacy of BMS-986165 with regard to measures of renal function and SLE activity
 
	
 
PRR at Week 24, defined as <math>\geq 50\%</math> reduction from baseline in 24-hour UPCR
 
CRR at Week 24, defined as both of the following:                             
 
24-hour UPCR <math>\leq 0.5</math> mg/mg
 
eGFR <math>\geq 60</math> mL/min or <math>\leq 20\%</math> decrease from baseline
 
 
 
CRR at Week 52
 
CRR + successful CS taper to <math>\leq 7.5</math> mg/day at Week 24
 
CRR + successful CS taper to <math>\leq 7.5</math> mg/day at Week 52
 
PRR at Week 52
 

AE = adverse event; C = complement; [redacted] CRR = complete renal response; CS = corticosteroid; [redacted] ECG = electrocardiogram; eGFR = estimated glomerular filtration rate; [redacted]  
[redacted] LN = lupus nephritis; NIH = National Institutes of Health; [redacted] OSS = Ohio SLE Study; [redacted]  
PRR = partial renal response; [redacted]  
[redacted] UPCR = urine protein:creatinine ratio

Note: 24-hour urine specimens will be used for the UPCR at baseline (Visit A4), Week 24 (Visit B7), and Week 52 (Visit B14).

Note: eGFR will be calculated using the Modification of Diet in Renal Disease (MDRD) equation

## 4 STUDY DESIGN

### 4.1 Overall Design

This is a 3-part, multicenter, randomized, double-blind study to evaluate the efficacy and safety of BMS-986165 in combination with background treatment with MMF in subjects with LN International Society of Nephrology/Renal Pathology Society (ISN/RPS) Class III or IV (alone or in combination with Class V). Subjects will be assessed for renal response after having received a total of at least 12 weeks (but  $\leq 24$  weeks) of treatment with MMF at a target dose of 1.5 to 3.0 g/day (refer to [Section 6.1](#) for further details regarding individual target dose). Subjects will receive 12 weeks of target-dose MMF in Part A of the study if they have not been taking target-dose MMF at screening. Subjects who have been taking target-dose MMF for  $\geq 1$  day but  $< 12$  weeks at screening will continue to receive target-dose MMF in Part A until they reach 12 weeks of total MMF treatment. Subjects who have been taking target-dose MMF for  $\geq 12$  weeks but  $\leq 24$  weeks at screening will enter the study at Visit A4 to immediately be assessed for renal response and entry into Part B.

Subjects with an inadequate renal response to MMF may be randomized to blinded study treatment BMS-986165 3 mg BID, BMS-986165 6 mg BID, or placebo BID, as add-on therapy to MMF in Part B. Inadequate response is defined as  $< 50\%$  reduction in 24-hour urine protein:creatinine ratio (UPCR) from the pre-MMF value (refer to [Section 4.1.2.2](#)) and a 24-hour UPCR  $\geq 1.0$  mg/mg. Randomized subjects will continue taking open-label MMF with or without corticosteroids. Randomization will be stratified by baseline (Visit A4) 24-hour UPCR ( $< 3.0$  mg/mg versus  $\geq 3.0$  mg/mg) and total cumulative intravenous (IV) corticosteroid (IV methylprednisolone or

parenteral equivalent) dose given in the 16 weeks before randomization (< 250 mg versus  $\geq$  250 mg).

The total duration of participation in the study is up to [REDACTED] weeks, which includes the following periods:

- Screening period: approximately 28 days (this period may be extended up to 5 days if needed to complete screening procedures, with approval of the [REDACTED] medical monitor)
- Treatment period:
  - Part A: Open-label MMF (1.5 to 3.0 g/day) run-in period of up to 12 weeks, depending on duration of treatment with MMF at the time of screening; see [Table 2](#) for the assessments during Part A
  - Approximately 1 week between the last visit in Part A (Visit A4) and the first visit in Part B (Visit B1)
  - Part B: Randomization followed by blinded study treatment for 52 weeks plus continued open-label MMF with or without corticosteroids (or just continued open-label MMF with or without corticosteroids for those who are not randomized); all subjects will attend study visits every 4 weeks and undergo assessments as indicated in [Table 3](#)
  - [REDACTED]
- A follow-up period of  $28 \pm 3$  days followed by an end-of-study visit

After a screening period of up to 28 days, eligible subjects will enter Part A of the study, an open-label MMF run-in period of up to 12 weeks. Subjects may continue taking MMF as previously prescribed (if at a dose of 1.5 to 3.0 g/day) until they reach 12 weeks of treatment or, if not receiving MMF or previously prescribed < 1.5 g/day, subjects will be either started on MMF when they enter Part A or titrated to a dose of 1.5 to 3.0 g/day for the full 12 weeks of Part A. Subjects who have been taking MMF at a dose of 1.5 to 3.0 g/day for  $\geq$  12 but  $\leq$  24 weeks at the time of screening will promptly be evaluated for continuation in Part B and for randomization. The suggested target dose of MMF at the first visit in Part B is 1.5 to 2.0 g/day (maximum 3.0 g/day) unless limited by intolerance or toxicity (refer to [Section 6.1](#) for further details regarding individual target dose).

After at least 12 weeks of open-label MMF treatment of at least 1.5 g/day (either only during Part A of the study or including previously prescribed MMF before and during screening), subjects

will be assessed to determine whether they meet the criteria to continue in Part B (see [Section 4.1.2.1](#)), and whether they meet the randomization criteria (see [Section 4.1.2.2](#)). Those subjects who meet all the criteria to continue in Part B and meet the randomization criteria will be assigned in a double-blind manner (1:1:1) to one of the following treatment groups:

- BMS-986165 3 mg BID + continued open-label MMF with or without corticosteroids
- BMS-986165 6 mg BID + continued open-label MMF with or without corticosteroids
- Placebo BID + continued open-label MMF with or without corticosteroids

Randomization will be stratified by baseline (Visit A4) 24-hour UPCR (< 3.0 mg/mg versus  $\geq$  3.0 mg/mg) and total cumulative IV corticosteroid (IV methylprednisolone or parenteral equivalent) dose given in the 16 weeks before randomization (< 250 mg versus  $\geq$  250 mg).

Subjects who meet the criteria to continue in Part B but do not meet the randomization criteria may continue on open-label MMF with or without corticosteroids during Part B and will attend the same visits every 4 weeks and have the same assessments as randomized subjects. These nonrandomized subjects will exit the study at the end of Part B.

Corticosteroids are permitted but not required in this study. Subjects who are taking corticosteroids will have their dose tapered (if possible) during Part B as described in [Section 6.6.1](#).

In Part B, subjects (randomized and nonrandomized) will attend study visits every 4 weeks through Week 52.

Optional renal biopsies may be performed at Week 52 [REDACTED], as well as at the end of treatment for subjects who discontinue early if discontinuation occurs after Week 24 of Part B. After the last treatment visit (Week 52 [REDACTED] or early discontinuation), subjects will attend a final end-of-study visit at the end of a 28-day follow-up period.

[figure not shown]
The study design schematic is presented in [Figure 1](#).

### Figure 1: Study Design: Part A and Part B

[figure not shown]
The study design schematic for the open-label MMF run-in period (Part A) and the 52-week Blinded Treatment Period (Part B) is presented below.

**Randomization Criteria:**

1. < 50% decrease in UPCR from screening (or historical value from start of MMF)
2. UPCR  $\geq$  1.0 mg/mg
3. Trough MPA concentration  $\geq$  1  $\mu$ g/mL
4. No more than 25 mg/day prednisone (or equivalent)
5. Continue to meet all I/E criteria

BID = twice daily; CS = corticosteroid; EOS = end-of-study; EOT = end-of-treatment; d = day; F/U = follow-up; I/E = inclusion/exclusion; LTE = Long-term Extension; MMF = mycophenolate mofetil; MPA = mycophenolic acid; PRR = partial renal response; R = randomization; UPCR = urine protein:creatinine ratio; Wk = week

#### 4.1.1 **Part A: Open-label Mycophenolate Mofetil Run-in Period**

All subjects who meet the study eligibility criteria will enter Part A of the study.

Subjects who are not already taking MMF will begin MMF and titrate to a dose of 1.5 to 3.0 g/day, and subjects who are taking < 1.5 g/day of MMF at screening will increase to a target dose of 1.5 to 3.0 g/day (refer to [Section 6.1](#) for further details about individual target dose) with or without corticosteroids. After 12 weeks of treatment with MMF at a dose of 1.5 to 3.0 g/day, they will be evaluated for continuation in Part B and for randomization.

Subjects who have been taking MMF at a dose of 1.5 to 3.0 g/day for  $\geq 1$  day but < 12 weeks at the time of screening will continue MMF in Part A until they have completed a total of 12 weeks of treatment at this dose (including weeks of MMF before entering Part A), and will then be evaluated for continuation in Part B and for randomization.

Subjects who have been taking MMF at a dose of 1.5 to 3.0 g/day for  $\geq 12$  but  $\leq 24$  weeks at the time of screening will promptly be evaluated for continuation in Part B and for randomization (Visit A4; including collection of a single 24-hour urine specimen; the other UPCR value will be the one from the 24-hour urine at screening) as soon as eligibility is confirmed.

Subjects who have been taking MMF at a dose of 1.5 to 3.0 g/day for > 24 weeks at the time of screening are not eligible to participate in the study.

Paths to enrollment based on the duration of MMF treatment at a dose of 1.5 to 3.0 g/day at the time of screening are shown in [Figure 3](#) and [Figure 4](#).

Subjects will attend up to 4 visits in Part A:

- Visit A1 (Day 1)
- Visit A2 (Week 4 of MMF  $\pm$  14 days)
- Visit A3 (Week 8 of MMF  $\pm$  14 days)
- Visit A4 (Week 12 of MMF  $\pm$  14 days)

**Note:** The  $\pm 14$ -day windows for Visit A2, Visit A3, and Visit A4 are used to allocate the subject's first Part A visit based on the subject's number of weeks on MMF; the actual visit dates subsequent to the first Part A visit should occur as close to the required timepoint (Week 4, Week 8, or Week 12) as possible, with a  $\pm 3$  day window to complete the visit.

[figure not shown]
Subjects who are not taking MMF during screening or who are taking < 1.5 g/day will attend all 4 visits in Part A. Subjects with  $\geq 1$  day but < 12 weeks of MMF at a dose of 1.5 to 3.0 g/day will continue their MMF treatment until they reach the corresponding Part A visit (A2, A3, or A4). Subjects whose duration of MMF therapy puts them between two Part A visits will "round up" to the next visit. For example, a subject with 6 weeks of MMF when entering Part A would start at Visit A3.

Subjects with  $\geq 12$  but  $\leq 24$  weeks of MMF at a dose of 1.5 to 3.0 g/day at the time of screening will enter Part A and attend Visit A4 to be assessed for continuation in Part B and for

randomization as soon as possible after study eligibility is confirmed. No subject will “round up” to Visit A4 unless they meet the minimum of 12 weeks  $\pm$  3 days of MMF as shown in [Table 2](#).

[figure not shown]
For premenopausal women, study visits and 24-hour urine collections should be scheduled, when possible, for times when they are not menstruating.

**Figure 3: Path to Enrollment for Subjects Not Taking Mycophenolate Mofetil or Who Are Taking Less Than 1.5 g/day at the Time of Screening**

LN = lupus nephritis; MMF = mycophenolate mofetil; mos = months

**Figure 4: Paths to Enrollment for Subjects with  $\geq 1$  Day but  $\leq 24$  Weeks of Mycophenolate Mofetil at a Dose of 1.5 to 3.0 g/day at the Time of Screening**

LN = lupus nephritis; MMF = mycophenolate mofetil; mos = months

#### **4.1.1.1 Evaluation for Continuation in Part B and for Randomization**

When subjects have completed 12 weeks of MMF treatment at a dose of 1.5 to 3.0 g/day, they will attend Visit A4 and will have assessments needed to determine whether they meet the criteria to continue in Part B and the randomization criteria. Samples and assessments will include the following:

- Spot UPCR from a first morning voided specimen (a second morning void may be used if the first morning void was not collected)
- Two 24-hour urine specimens (one approximately 7 to 10 days before Visit A4 and the other just before Visit A4); if the UPCR values between these specimens differ by > 20%, a third 24-hour urine specimen will be collected to determine the average value; the third sample (if needed) should be collected as soon as possible but no more than 10 days after the first two results are reported
- Trough plasma mycophenolic acid (MPA) concentration
- Investigator determination of whether subject is taking and tolerating target-dose MMF (1.5 to 3.0 g/day) and likely to continue to tolerate the target dose through Week 52

For subjects with 12 to 24 weeks of MMF at a dose of 1.5 to 3.0 g/day at the time of screening, a 24-hour urine specimen should be collected and Visit A4 should occur as soon as possible after eligibility is confirmed so that they will not exceed 28 weeks of MMF at a dose of 1.5 to 3.0 g/day at the time of randomization. Because 2 to 4 weeks may be required to complete the screening evaluations to determine eligibility to participate in the study, these subjects will likely have the randomization assessment visit at Week 26 or 27 of MMF, and the randomization visit (Visit B1) no later than 28 weeks of MMF. For these subjects, their UPCR for randomization will be calculated from the 24-hour urine specimens collected at screening and Visit A4.

#### **4.1.2 Part B: Randomized, Blinded Treatment Period Through Week 52**

No more than 10 days after Visit A4, subjects should attend the randomization visit (Visit B1). Medical monitor approval is required if more than 10 days is necessary. At this visit, the laboratory results from Visit A4 will be evaluated to determine whether the subject meets the criteria to continue in Part B, and whether they meet the randomization criteria.

Subjects who do not meet the criteria to continue in Part B will exit the study.

Subjects who meet the criteria to continue in Part B but do not meet the randomization criteria may continue on open-label MMF.

Subjects who meet the criteria to continue in Part B and the randomization criteria will be randomized to blinded study treatment plus continued MMF.

For premenopausal women, study visits and 24-hour urine collections should be scheduled, when possible, for times when they are not menstruating.

All subjects in Part B will then attend study visits every 4 weeks ( $\pm$  3 days) through Week 52.

[figure not shown]
#### **4.1.2.1 Criteria to Continue in Part B With or Without Randomization**

1. Trough MPA concentration  $\geq 1$   $\mu\text{g/mL}$  (this sample will be collected at Visit A3 to allow sufficient time for analysis and reporting of result; for subjects with  $\geq 12$  weeks of MMF at the time of screening, the screening value will be used)
2. The corticosteroid dose (if any) at Visit B1 must not exceed 25 mg/day of prednisone (or equivalent dose of other corticosteroid; see [APPENDIX 6](#))
3. The subject continues to meet all study eligibility criteria (see [Section 5](#)), including the blood pressure requirement (see Exclusion Criterion 2b in [Section 5.2](#))
4. The subject is taking and tolerating target-dose MMF (1.5 to 3.0 g/day) and likely to continue to tolerate the target dose through Week 52

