**Table 1: Screening Procedures and Assessments for Protocol IM011073**

Procedure/assessment	Screening (from D-28)	Notes
APAs	X	aCl, LA, anti-β2GP1 (IgA, IgG, and IgM)
TSH	X	Free thyroxine will be assessed only if the TSH is abnormal
UA with microscopic examination	X	Clean-catch specimen; if the UA is positive for leukocytes, blood, or bacteria, a urine culture should be performed if appropriate
UPCR	X	First morning voided specimen (if the first morning void was not collected, the second morning void may be used) Subjects will also collect a 24-hour urine sample for UPCR.
Urine pregnancy test	X	Required for WOCBP only
FSH	X	If needed to confirm postmenopausal status
TB Screening	X	Refer to Section 8.7.2
IGRA assay	X	For TB screening
Other procedures if all other eligibility criteria are met		
Renal biopsy	X	Documented results within 3 or 6 months before screening may be used, if subject’s screening UPCR value is ≥ 1 mg/mg or ≥ 1.5 mg/mg, respectively. Refer to Section 5.1
Chest x-ray (PA and lateral)	X	For TB screening; if available, a documented result of an X-ray or CT scan of the chest within 6 months before screening may be used

aCl = anticardiolipin antibody; ANA = antinuclear antibody; Sm = Smith; APA = antiphospholipid antibody; β2GP1 = beta-2 glycoprotein 1; BMI = body mass index; C = complement; [REDACTED] CT = computed tomography; D = Day; DNA = deoxyribonucleic acid; [REDACTED] ECG = electrocardiogram; FSH = follicle-stimulating hormone; HBc = hepatitis B core; HBs = hepatitis B surface; HBsAg = hepatitis B surface antigen; HBV = hepatitis B virus; HCV = hepatitis C virus; HIV = human immunodeficiency virus; hsCRP = high-sensitivity C-reactive protein; ICF = informed consent form; [REDACTED] Ig = immunoglobulin; IGRA = interferon-gamma release assay; [REDACTED] IRT = interactive response technology; [REDACTED] LN = lupus nephritis; MMF = mycophenolate mofetil; MPA = mycophenolic acid; [REDACTED] PA = posterior-anterior; RNA = ribonucleic acid; [REDACTED] SAE = serious adverse event; SLE = systemic lupus erythematosus; SLICC = Systemic Lupus Erythematosus International Collaborating Clinics; [REDACTED] TB = tuberculosis; TSH = thyroid-stimulating hormone; UA = urinalysis; UPCR = urine protein:creatinine ratio; US = United States; WOCBP = women of childbearing potential

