**Table 3: Procedures and Assessments in Part B of IM011073 (52-Week Blinded Treatment Period)**

Visit Number	B1	B2	B3	B4	B5	B6	B7	B8	B9	B10	B11	B12	B13	B14/ EOT a	B15 a	Notes
Study Week/Day	D1	W4 D29 ±3d	W8 D57 ±3d	W12 D85 ±3d	W16 D113 ±3d	W20 D141 ±3d	W24 D169 ±3d	W28 D197 ±3d	W32 D225 ±3d	W36 D253 ±3d	W40 D281 ±3d	W44 D309 ±3d	W48 D337 ±3d	W52 D365 ±3d	28-D FU ±3d	The final study visit (for noncontinuing subjects) will occur 28d±3d after the visit at W52
Confirm study eligibility criteria are still met	X															
Evaluate for randomization	X															
Body weight & vital signs	X	X	X	X	X	X	X	X	X	X	X	X	X	X	X	BP and HR should be measured after the subject has been sitting quietly for at least 5 minutes
Complete physical examination	X	X	X	X	X	X	X	X	X	X	X	X	X	X	X	
Concomitant medications	X	X	X	X	X	X	X	X	X	X	X	X	X	X	X	
12-lead ECG	X	X	X				X						X	X		
AEs and SAEs	X	X	X	X	X	X	X	X	X	X	X	X	X	X	X	Section 8.5
Subject Status Evaluation							X									Section 7.2
Indices of disease activity and damageb																
rSFI		X	X	X	X	X	X	X	X	X	X	X	X	X	X	All systems except renal; clinical component only (not treatment) APPENDIX 17
OSS Flare Index		X	X	X	X	X	X	X	X	X	X	X	X	X	X	APPENDIX 16

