#### **4.1.2.2 Randomization Criteria**

Subjects who meet the criteria to continue in Part B and meet the following criteria will be eligible to be randomized to add-on therapy with blinded study treatment:

1.  $< 50\%$  reduction in UPCR from the pre-MMF value (either the value from study screening or historical value before the start of MMF for those already on MMF at the time of screening) to the value at Visit A4. For the subjects who are on MMF at a dose of  $< 1.5$  g/day at the time of screening, the pre-MMF value will be taken from screening
2. UPCR  $\geq 1.0$  mg/mg based on the two 24-hour urine specimens from approximately 7 to 10 days before Visit A4, and just before Visit A4; if the UPCR values differ by  $> 20\%$ , a third 24-hour urine specimen will be collected to determine the average; the third specimen (if needed) should be collected as soon as possible but no more than 10 days after the first two results are reported, as described in [Section 8.4.1](#)

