#### 2) SLE Disease Characteristics

- a. Meets the SLICC criteria for SLE (see [APPENDIX 5](#))
- b. Renal biopsy confirming a histologic diagnosis of active LN ISN/RPS Classes III (A or A/C), IV-S (A or A/C), or IV-G (A or A/C); or Class V (in combination with Class III or IV) (see [APPENDIX 12](#)):
  - i. N/A per Revised Protocol 10
  - ii. N/A per Revised Protocol 10
  - iii. If a biopsy was done within  $\leq 6$  months before screening, sites/laboratories have the option of providing at least one of the following samples: Renal fresh biopsy; renal historical biopsy (Formalin Fixed Paraffin Embedded block); renal archival slides; or digital image slides (refer to the Arkana laboratory manual for further details)
  - iv. If a biopsy has not been done within 6 months before screening and the subject meets all other eligibility criteria, a biopsy will be performed as part of the study
- c. N/A per Revised Protocol 10

- d. UPCR  $\geq$  1.5 mg/mg (for subjects with biopsies taken  $\leq$  6 months prior to screening) or UPCR  $\geq$  1 mg/mg (for subjects with biopsies taken  $\leq$  3 months prior to screening) assessed with a 24-hour urine specimen

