### 6.6.1 **Corticosteroid Tapering and Corticosteroid Rescue in Part B**

Corticosteroids are permitted but not required in this study. One of the criteria to continue in the study during Part B is that the corticosteroid dose (if any) must not exceed 25 mg/day of prednisone or prednisone equivalent. Management of corticosteroids including initiation and dosing in Part A will be at the discretion of the investigator. All corticosteroid doses in this section of the protocol refer to prednisone. See [APPENDIX 6](#) for prednisone-equivalent doses of other corticosteroids.

For subjects deemed by the investigator to be appropriate for corticosteroid tapering, this section includes a guideline and a suggested sequence of tapering.

Subjects will be assessed for SLE flare at study visits every 4 weeks throughout Part B. Flare assessments will be made in comparison to the previous visit. Corticosteroid doses may be tapered at the time of a study visit, and at the investigator's discretion, subjects may be instructed to adjust the corticosteroid dose in between study visits. For example, at a study visit, an investigator may taper the dose and instruct a subject to taper again to the next lower dose (to be specified) 2 weeks later if they are feeling well. Likewise, after a study visit at which the dose is tapered, an investigator may instruct the subject to resume the previous dose before the next study visit if needed because of intolerance.

Subjects who respond to MMF during Part A and therefore do not meet the randomization criteria, but who continue open-label MMF in Part B will follow the same corticosteroid taper.

Randomized subjects taking corticosteroids will be required to have their dose tapered during Part B unless there is evidence of increased extrarenal disease activity as assessed by the rSFI (clinical component only; the renal system will not be assessed with the rSFI; see [APPENDIX 17](#)) or worsening or unstable renal findings per the OSS Flare Index (see [APPENDIX 16](#)) as follows:

- If either flare index indicates a moderate or severe flare, the corticosteroid dose should not be tapered
- If either flare index indicates a mild flare, or if there is no flare but there is another reason not to taper the corticosteroid dose, the investigator must contact CRS, which will refer the case to the study-designated nephrology or rheumatology Therapeutic Expert for additional review

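### Does the eligibility re-check at Part B entry re-impose the inclusion UPCR threshold at Visit A4?

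*Combined protocol and SAP*

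**What the plan says.** Entry to Part B, randomized or not, depends on Section 4.1.2.1. Its item 3 requires that "The subject continues to meet all study eligibility criteria". It names the blood pressure limit as included and names nothing as excepted. Section 4.1.2 gives the consequence of failing: "Subjects who do not meet the criteria to continue in Part B will exit the study". Table 3 schedules the re-check at Visit B1 ("Confirm study eligibility criteria are still met"), and the synopsis schema and Figure 1 list it as randomization criterion 5 ("Continue to meet all I/E criteria").

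Inclusion 2d in Section 5.1 asks for a UPCR of at least 1.5 mg/mg when the biopsy is up to 6 months old, or at least 1 mg/mg when it is up to 3 months old. It ends "3 months prior to screening) assessed with a 24-hour urine specimen". It dates the biopsy but gives no visit for the UPCR. The biopsy note in Table 1, which refers to Section 5.1, does give one: an existing biopsy may be used if the "screening UPCR value is ≥ 1 mg/mg or ≥ 1.5 mg/mg, respectively".

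Section 4.1.2.2 then requires a reduction of less than 50% from the pre-MMF value and a UPCR of at least 1.0 mg/mg, "based on the two 24-hour urine specimens from approximately 7 to 10 days before Visit A4, and just before Visit A4". Section 6.6.1 sets the steroid taper for "Subjects who respond to MMF during Part A and therefore do not meet the randomization criteria, but who continue open-label MMF in Part B".

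**The concern.** Taken at its word, item 3 covers every Section 5 criterion, and 2d is one of them. Two groups then appear to be treated inconsistently.

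- **Randomization.** A subject with an older biopsy can have an inadequate response by both tests in 4.1.2.2 and still be below 1.5 mg/mg at Visit A4. That subject looks eligible under 4.1.2.2 and ineligible under 4.1.2.1.
- **Open-label continuation.** A good response to MMF lowers the UPCR. Re-applying 2d would send home responders below their threshold, although Section 6.6.1 expects some responders to stay on open-label MMF.

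At stake would be who is randomized among the roughly 78 planned, and whether the open-label summaries in Section 9.4 lose the subjects with the lowest proteinuria.

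**Working it through.** The plan states no figure on this point, so there is nothing to reproduce. The check is the logic of the thresholds, followed by a comparison of the sections.

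**Inputs.** T is the 2d threshold (1.5 or 1.0 mg/mg, Section 5.1). s is the screening UPCR, taken here as the pre-MMF value. a is the Visit A4 UPCR. Section 4.1.2.2 requires a ≥ 1.0 and 1 − a/s < 0.50, that is s < 2a.

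**Step 1: randomization if 2d is re-applied.** A clash needs 1.0 ≤ a < T together with T ≤ s < 2a.

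- T = 1.0: the condition 1.0 ≤ a < 1.0 is empty, so there is no clash.
- T = 1.5: a = 1.0 gives s from 1.5 to below 2.0; a = 1.2 gives 1.5 to below 2.4; a = 1.49 gives 1.5 to below 2.98. Since a < 1.5, s is always below 2 × 1.5 = 3.0.

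**Step 2: responders if 2d is re-applied.** A reduction of at least 50% means a ≤ s/2, so a is certain to be below T when s < 2T: s < 2.0 for T = 1.0 and s < 3.0 for T = 1.5. Above those values only deeper reductions take a below T.

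| s to a (mg/mg) | Reduction | Meets 4.1.2.2 | a ≥ 1.0 | a ≥ 1.5 |
|---|---|---|---|---|
| 2.0 to 1.2 | 1 − 1.2/2.0 = 40% | yes | yes | no |
| 1.8 to 0.8 | 1 − 0.8/1.8 = 56% | no | no | no |
| 2.8 to 1.3 | 1 − 1.3/2.8 = 54% | no | yes | no |
| 4.0 to 1.8 | 1 − 1.8/4.0 = 55% | no | yes | yes |

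**Step 3: limits of these bounds.** For subjects already on target-dose MMF at screening, the pre-MMF value is historical. The condition that it be below 2a still holds, but the lower end of 1.5 no longer follows from 2d. For those with at least 12 weeks of MMF, the UPCR used for randomization combines the screening and Visit A4 specimens (Section 4.1.1.1). Subjects biopsied on study under inclusion 2b(iv) have no biopsy in either 2d window, so 2d states no threshold for them.

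**Step 4: do the sections contradict each other?** Section 4.1.2.2 opens by requiring the continuation criteria as well as its own, so the tests are cumulative. If 2d is re-applied, the subject going from 2.0 to 1.2 fails one required test and exits. If 2d is a screening test, the same subject is randomized, provided the other criteria are met. Each reading gives one answer, so the open question is the scope of item 3. Sections 4.1 and 4.1.2 say that non-randomized subjects may continue, and Section 6.6.1 describes those who do. None of them promises continuation to every responder.

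**Step 5: which reading fits the rest of the protocol?**

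- Table 1 states the same two thresholds for the screening UPCR and refers to Section 5.1.
- With 2d re-applied, item 3 would already guarantee a ≥ 1.0 or a ≥ 1.5, and item 2 of 4.1.2.2 would be idle for everyone with a 2d threshold.
- Section 4.1 defines inadequate response with one floor of 1.0 mg/mg, whatever the age of the biopsy.
- Several criteria meant to hold at randomization say so: inclusion 3b and exclusions 2b, 2q and 4e. Inclusion 2d does not.

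**Step 6: effect on the analysis.** Either reading acts before randomization and on baseline information, so the arms remain comparable. The Full Analysis Set is all randomized subjects (Section 9.2). Everyone affected in Step 1 has a Visit A4 UPCR below 1.5 mg/mg and so falls in the < 3.0 mg/mg stratum.

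**The case for a change.** The best case for a change is that the operative text should be explicit. Exclusions 1b and 2c carry a screening label and 2d does not. A label would not settle it alone, because exclusion 2b is worded as a screening blood pressure and is still re-checked. Section 4.1.2 says Visit A4 laboratory results decide continuation, and item 3 is the continuation criterion those results would inform. Section 8 allows no waivers. Central confirmation under Section 5 is required for randomization; it is not stated for open-label continuation.

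Part of this stands: 2d does lack a visit, and Section 5 does not say who rules on open-label continuation. The rest carries less weight. Exclusion 2b contains its own clause for the time of randomization, which explains why item 3 names it. Visit A4 results can inform item 3 without the UPCR, since exclusion 5a covers clinically significant laboratory deviations and names no visit. Reading 2d as Table 1 does is interpretation, so it needs no waiver.

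**Conclusion.** No change to the plan is needed. The wording gap is real but small: 2d does not say that its UPCR is the screening value, and item 3 does not say whether 2d is re-checked. Table 1 supplies the missing visit, and the alternative reading would make a listed randomization criterion redundant on both biopsy branches.

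If 2d were re-applied, the randomization effect would be limited to older-biopsy subjects with a Visit A4 UPCR of 1.0 to below 1.5 mg/mg and, where screening is the pre-MMF value, a screening UPCR of 1.5 to below 3.0 mg/mg. The open-label group would be reduced but not emptied, as the fall from 4.0 to 1.8 shows. The documents do not allow a percentage for either group.

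The conclusion assumes that central reviewers and the medical monitor, who must confirm eligibility before any randomization, read 2d as Table 1 does, and that sites do the same for open-label continuation. If they did not, the mix of subjects entering Part B would shift, but the randomized comparison with placebo would remain valid for those randomized.
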